6 STATISTICAL METHODOLOGY

6.1 General Considerations

Efficacy data will be summarized for each age group (children [5 to <12 years of age] and adolescents [12 to <18 years of age]) by treatment group and visit, and safety data will be summarized for each age group and overall, by treatment group and visit, unless otherwise specified.

In general, continuous data will be summarized descriptively including the number of subjects (n), mean, standard deviation (SD), median, minimum and maximum. Categorical data will be summarized by frequencies and percentages. Percentages by categories will be based on the number of subjects with no missing data, i.e. the percentages for the non-missing categories will add up to 100%.

All statistical comparisons will be conducted using 2-sided tests at the 10% significance level unless stated otherwise. All null hypotheses will be of no treatment difference, all alternative hypotheses will be two-sided, unless specifically stated otherwise.

All data summarization and analyses will be performed using SAS® Version 9.4 or higher on Red Hat Enterprise Linux. Specifications for table, figure, and data listing formats can be found in the TLF specifications.

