6.5.2 Clinical Laboratory Evaluation

The baseline value will be the last non-missing value taken on or prior to first dose of study drug.

Quantitative clinical laboratory variables, i.e., hematology, biochemistry, and urinalysis will be summarized using mean, standard deviation, median, minimum and maximum, for each age group and overall, by treatment group and visit.

Summary of laboratory values will be presented for visit 1, 3, 5, 7 and 8 (EoS)], and for EoT values.

Additionally, a within-subject change will be calculated as the post-baseline measurement minus the baseline measurement and summarized in the same way. Each laboratory result will be classified as low (L), normal (N), or high (H) at each visit according to the laboratory supplied reference ranges.

The number and percentage of subjects below and above reference range will be summarized, for each age group and overall, by treatment group and visit.

Frequency tabulations of qualitative clinical laboratory variables (urinalysis) will be presented, for each age group and overall, by treatment group and visit.

Shifts from baseline to week 4, week 12 and EoT will be summarized by two types of shift tables:

- Shift tables of reference range (low, normal, high) changes from baseline to week 12 and to EoT, and
- Summary shifts of reference range changes from baseline to week 4, week 12 and EoT.

These shifts are categorized as:

- "Shift to Low": shift from normal or high to low
- "Shift to High": shift from normal or low to high
- "Categorized Increase": shift from low to normal or from normal to high
- "Categorized No Change": value stays in the same reference range
- "Categorized Decrease": shift from high to normal or from normal to low.

All clinical laboratory data collected during the study and variables derived from it will be listed using SAF.

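### The laboratory shift summary leaves low-to-high and high-to-low out of Categorized Increase and Decrease, so the direction categories undercount and can total less than 100%

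*SAP*

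**What the plan says.** SAP 6.5.2 sets up three classes for every laboratory parameter: "Each laboratory result will be classified as low (L), normal (N), or high (H) at each visit". Shifts from baseline are then shown in two types of table. The first is the full cross-tabulation, for week 12 and EoT only: "Shift tables of reference range (low, normal, high) changes from baseline to week 12 and to EoT, and". The second is a condensed summary for week 4, week 12 and EoT, with five lines:

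- *Categorized Increase* is limited to a "shift from low to normal or from normal to high".
- *Categorized Decrease* mirrors it and is limited to a "shift from high to normal or from normal to low".
- *Categorized No Change* applies when the class is the same at both time points.
- *Shift to High* takes in every subject who ends high after starting in another class: "shift from normal or low to high".
- *Shift to Low* does the same for subjects who end low: "shift from normal or high to low".

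SAP 6.1 gives a general convention for categorical summaries. Percentages are taken over subjects with non-missing data, so that "the percentages for the non-missing categories will add up to 100" percent.

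Protocol 9.5.2 asks only that shifts relative to normal ranges be tabulated for each treatment-period visit. It does not define the categories.

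**The concern.** The five lines mix two ways of sorting the same change. *Shift to Low* and *Shift to High* sort by where the value ends up. Increase, No Change and Decrease sort by direction of movement. The destination lines explicitly include the two-step changes, so the authors had them in mind, but the direction lines do not. Programmed as written, a subject who moves from below the range to above it is not an increase, not a decrease and not unchanged.

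What is at stake is the readability and internal consistency of a safety table. The direction lines would understate increases and decreases by exactly the subjects with the widest movement across the range. At week 12 and EoT they would also disagree with a count of increases and decreases taken from the full table.

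**Working it through.** The plan states no figure to reproduce; the check is an enumeration.

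**Inputs.** Three classes (L, N, H) and the five definitions, all from SAP 6.5.2. Three classes at baseline and three afterwards give 3 × 3 = 9 transitions.

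**Mapping as written.**

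| Transition | Destination lines | Direction lines |
|---|---|---|
| L→L | none | No Change |
| L→N | none | Increase |
| L→H | Shift to High | **none** |
| N→L | Shift to Low | Decrease |
| N→N | none | No Change |
| N→H | Shift to High | Increase |
| H→L | Shift to Low | **none** |
| H→N | none | Decrease |
| H→H | none | No Change |

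**Coverage of the direction lines.** Increase 2 + No Change 3 + Decrease 2 = 7 of 9. The two missing transitions are L→H and H→L. The shortfall in the three-line total is therefore the number of subjects with L→H plus the number with H→L. It is zero when neither occurs.

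**Coverage of all five lines.** 2 + 2 + 2 + 3 + 2 = 11 assignments for 9 transitions. Every transition is in at least one line. N→H and N→L are each in two.

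**Size of one two-step shift.** SAP 3 plans at least 92 children and 16 adolescents on mirabegron. If every one of them has a baseline and a post-baseline value, one such subject is:

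- 1/92 = 1.1% of the children's column, so the direction lines total 91/92 = 98.9%;
- 1/16 = 6.25%, about 6.3%, of the adolescents' column, so they total 15/16 = 93.75%.

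**Where the two-step shifts can be seen.**

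- Week 12 and EoT: in their own cells of the full table.
- Week 4: the full table is not planned. In the condensed summary L→H is pooled with N→H, and H→L with N→L.

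**After the change proposed below.** Increase 3 + No Change 3 + Decrease 3 = 9, each transition once, so the direction lines total 100%. The destination lines still overlap them: N→H and L→H also appear under *Shift to High*, and N→L and H→L under *Shift to Low*.

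**The case against.** The strongest reply is that nothing is lost. *Shift to High* and *Shift to Low* name the two-step changes, so all nine transitions have a home in the list. A reader might infer that the largest shifts fall in no category; the SAP's own definitions rule that out.

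The SAP also never says that Increase, No Change and Decrease form an exhaustive set. The list as a whole overlaps and was not built to total 100%. The sentence in SAP 6.1 is a general rule about denominators and does not sensibly govern overlapping lines. A reader might infer a flat conflict between 6.5.2 and 6.1; that goes too far. The convention bears at most on the three direction lines, and only when a two-step shift occurs.

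Finally, other outputs in 6.5.2 carry the information: the full table at week 12 and EoT, counts below and above range by visit, within-subject changes, and listings of all laboratory data. No support exists for inferring that a safety signal would be hidden.

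All of this stands, and it limits the point. It does not remove it. Increase, No Change and Decrease read as a complete description of direction, and no ordinary meaning of increase excludes a move from low to high. Having the same subject under *Shift to High* does not correct the count of increases.

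**Conclusion.** The point holds in a narrow form. The direction lines in SAP 6.5.2 omit low to high and high to low, so they undercount increases and decreases, and total less than 100%, whenever such a shift occurs. The two-step shifts are still counted under *Shift to High* and *Shift to Low*. The full table shows them at week 12 and EoT, but no planned summary table separates them from one-step shifts at week 4.

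The effect is minor: a descriptive safety table, with no bearing on an efficacy endpoint or a test. The percentages above rest on the planned minimum numbers on mirabegron; the denominators will be the subjects with both values. They give the effect of a single subject, not an expected frequency, because the documents give no rate for two-step shifts. Using the planned total of 184 + 32 = 216 would be misleading, since the tables are presented by treatment group.

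**What to change.** In SAP 6.5.2:

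- define *Categorized Increase* as low to normal, low to high, or normal to high;
- define *Categorized Decrease* as high to normal, high to low, or normal to low;
- add one sentence stating that *Shift to Low* / *Shift to High* is a separate grouping that overlaps the direction categories, so the five lines are not expected to total 100%.

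The cost is two phrases and one sentence in the SAP, plus the matching change in the table program. No new data are needed. No protocol amendment is needed either, because Protocol 9.5.2 does not define the categories. SAP 1 allows revisions up to database hard lock, so the edit should be made before then.

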6.5.2.1 Central and Local Laboratory Data

In this study laboratory data may come from a central laboratory or a local laboratory, see Table 12 of the protocol.

For summarizing the data of a laboratory parameter the data from the local laboratory will be transformed. First all data from the parameter assessed in the local laboratory will be transformed into SI units. Next local laboratory data will be transformed according to the transformation formula below. Let x be the value of the laboratory parameter from the local laboratory, ULNL the upper limit of the normal range of the local laboratory, and ULNC the upper limit of the normal range of central laboratory then the transformed value (t) from the local laboratory is:

$$t = x.\frac{ULNC}{ULNL}$$
 (Scale normalization, Karvanen et al.)

This value t will be used for reporting laboratory values.

The results from the local laboratory will be used to determine whether a result is outside the normal range.

6.5.2.2 Liver Safety Assessment

The liver safety assessments will be summarized by the categories below based on the measurements from Alkaline Phosphatase (ALP), Alanine Transaminase (ALT), total bilirubin, Aspartate Transaminase (AST) and their combination. These parameters will be based on measurements from a central laboratory.

The subject's highest value during the investigational period will be used.

- ALT >3xULN, >5xULN, >10xULN, >20xULN
- AST >3xULN, >5xULN, >10xULN, >20xULN
- ALT or AST >3xULN, >5xULN, >10xULN, >20xULN
- ALP > 1.5 xULN
- Total Bilirubin >2xULN
- (ALT or AST >3xULN) and Total Bilirubin >2xULN
- (ALT or AST >3xULN) and ALP <2xULN and Total Bilirubin >2xULN

The last 2 criteria where 2 or more parameters are evaluated will be with the measurements on the same day or up to 1 day apart (Samples to be taken simultaneously or within a maximum of 24 hours).

The denominator for each criterion will be the number of subjects who have at least one value during the investigational period. The number and percentage of subjects meeting the criteria during the investigational period will be summarized, within and across age group by treatment group.

A scatter plot of Peak AST or ALT data vs. Peak Total Bilirubin data will be presented for mirabegron subjects. Data will be presented as fractions of the ULN. In this scatter plot the area for Hy's Law will be presented, where ALT or AST >3xULN and Total bilirubin > 2xULN (ALT, ALT and Total Bilirubin from same blood sample or within a maximum of 24 hours). The area for hyperbilirubinemia (ALT and AST <3xULN and Total bilirubin >2xULN), Temple's corollary (ALT or AST >3xULN and Total bilirubin < 2xULN) will also be presented in this scatter plot.

Laboratory data will be provided in listing format by country, site and subject for the SAF.

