- Site personnel have temporarily relocated the conduct of the study to a location that place a burden on the participant with respect to time and travel

11 Feb 2021 Astellas Page 108 of 157

EudraCT number 2016-001767-37

- CONFIDENTIAL -

Participant(s) have temporarily relocated from the current study site to an alternate study site to avoid placing a burden on the participant with respect to travel

- Participant(s) have temporarily relocated from their home location and the new distances from the site would cause undue burden with respect to time and travel
- Participant has risk factors for which traveling to the site poses an additional risk to the participant's health and safety

Adherence to the original protocol as reflected in the Schedule of Assessments [Table 1] is expected, where plausible, in the case of a crisis. The alternate measures as noted in [Table 12] below are only permissible in the event of a crisis, and after discussing the need with the Astellas medical monitor to implement the alternate measures. This is to allow for continuity of receiving IP and maintaining critical safety and efficacy assessments for patients participating in the study at a time of crisis.

If one or more of the alternate measures noted below is implemented for a participant, the site should document in the participant's source document the justification for implementing the alternate measure and the actual alternate measures that were implemented, along with the corresponding time point(s).

EudraCT number 2016-001767-37

- CONFIDENTIAL -

Table 12 Alternate Schedule of Assessments in Response to a Crisis

| | | Γ | od | Follow-up Period (2 weeks) | | | |
|-------------------------------------|--|--------------------|---------------------------|----------------------------|---------------------------|-------------------------------|---------------------------------|
| | | Visit 3 | Visit 4 | Visit 5 | Visit 6 | Visit 7 | Visit 8 |
| Critical Assessments | Alternate Approach(es) | Week 0 Baseline | Week 2 TC ^a | Week 4 | Week 8 TC ^a | Week 12 (EoT) ^b | Week 14 (EoS) ^{b,c} |
| | | Day -1 | Day 14 (± 3 days) | Day 28 (± 3 days) | Day 56 (± 3 days) | Day 84 (± 3 days) | Day 98 (+ 3 days) |
| Previous and Concomitant Medication | Remote/Virtual/Telemedicine Visits allowed. Please refer to protocol schedule of assessments. | X | X | X | X | X | X |

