| Physical Examination | The exam can be done at a local clinic and the results submitted to PI. | | | X | | X | |
| Height and Body Weight | Can be obtained at a local clinic or at home | X | | | | X | |
| Dose Titration ^d | Courier service directly to subject. Titration to occur based on PI's evaluation via phone. For tablets: subject to take spare 25 mg tablets until 50 mg wallet is delivered via courier. | | | X | | | |
| Dispense IP ^e | Courier service directly to subject | X | | X | | | |
| Drug Accountability | Used product can be shipped back to site via courier. | X | | | | X | |
| Vital Signs ^f | Can be performed at a local clinic and results submitted to PI for evaluation OR Blood pressure and pulse collected via SBPM and temperature collected at home and reported to site (respiration rate missing). | X | | X | | X | X |
| SBPM ^g | Will be sent to subject's home address | X | X | X | X | X | |
| Table continued on next page | | I. | 1 | 1 | I | | 1 |

EudraCT number 2016-001767-37

- CONFIDENTIAL -

| | | Γ | Follow-up Period (2 weeks) | | | | |
|--|--|--------------------|-------------------------------|-------------------|---------------------------|-------------------------------|---------------------------------|
| | | Visit 3 | Visit 4 | Visit 5 | Visit 6 | Visit 7 | Visit 8 |
| Critical Assessments | Alternate Approach(es) | Week 0 Baseline | Week 2 TC ^a | Week 4 | Week 8 TC ^a | Week 12 (EoT) ^b | Week 14 (EoS) ^{b,c} |
| | | Day -1 | Day 14 (± 3 days) | Day 28 (± 3 days) | Day 56 (± 3 days) | Day 84 (± 3 days) | Day 98 (+ 3 days) |
| Routine 12-lead ECG ^f | ECG testing can be completed at local clinic. | X | | X | | X | |
| Clinical Laboratory Tests (Hematology and Biochemistry) ^h | Visit collection of samples at local facility acceptable if results can be made available to investigative site. | Xi | | X | | X | X ⁱ |
| Clinical Laboratory Tests (Urinalysis) ^h | Visit collection of samples at local facility acceptable if results can be made available to investigative site. | Xi | | X | | X | Xi |
| Pregnancy Test ⁱ | Visit collection of samples at local facility acceptable if results can be made available to investigative site. | X | | X | | X | X |
| AEs | Remote/Virtual/Telemedicine Visits allowed. Please refer to protocol schedule of assessments. | X | X | X | X | X | X |
| Bladder e-diary | Will be sent to subject's home address | X | X | X | X | X | |

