5.4.3 Clinical Laboratory Variables

Hematology, biochemistry and urinalysis assessments will be taken at visit 1/week -4 (screening), visit 5/week 4, and visit 7/week 12 (EoT). Additional hematology, biochemistry and urinalysis tests will be performed at visit 3/week 0 (baseline), and visit 8/week 14 (EoS) only if an AE related to hematology, biochemistry or urinalysis parameters occurred since the previous visit or at the discretion of the investigator.

All clinical laboratory assessments will be performed at a central laboratory or at a local laboratory if results can be made available to the investigative site (see protocol, Appendix 12.23, Table 11), except for urine pregnancy testing and urinalysis (urinalysis dipstick), which will be performed at a local laboratory. Pregnancy test in females of child bearing potential will be performed in serum at screening, at baseline, visit 5/week 4, visit 7/week 12 (EoT), and visit 8/week 14 (EoS).

Additional hematology, biochemistry and urinalysis (UA dipstick) tests will be performed at visit 3/week 0 (baseline), visit 5/week 4 and visit 8/week 14 (EoS) only if an AE related to hematology, biochemistry or urinalysis parameters occurred since the previous visit or at the discretion of the investigator. If any of the clinical laboratory tests results are outside the normal range at any scheduled time point during the study, the investigator may decide to repeat the test(s) on new samples. The clinical relevance of the abnormal results will be documented. Clinically relevant changes will be recorded as AEs (see Section 7.3 of protocol: Adverse Events and Other Safety Aspects).

The laboratory parameters that will be assessed during the conduct of the study are listed in Table 5.

Hematology	Biochemistry	Urinalysis			
Hematocrit	Albumin	Leukocyte esterase			
Hemoglobin	Alanine aminotransferase	Nitrites			
Mean corpuscular volume	Alkaline phosphatase	pH			
Mean corpuscular hemoglobin	Aspartate aminotransferase	Protein			
Mean corpuscular hemoglobin	Bicarbonate	Red blood cells			
concentration	Blood urea nitrogen				
Platelets	Calcium				
Red blood cell count	Chloride				
White blood cell count	Corrected serum calcium				
White blood cell count differential	Creatinine				
	Creatinine kinase				
	Glucose				
	Lactate dehydrogenase				
	Magnesium				
	Phosphate				
	Potassium				
	Serum hCG for female subjects				
	Sodium				
	Total bilirubin (total and direct)				
	Total protein				

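### The SAP's liver categories and Hy's Law counts use central-laboratory values only, so an elevation seen only in a permitted local sample would be missing from those tables

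*SAP*

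**What the plan says.** SAP 6.5.2.2 (Liver Safety Assessment) defines the ALT, AST, ALP and bilirubin categories and two combined criteria, all as multiples of the ULN. Three of its rules matter here:

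- Source: "These parameters will be based on measurements from a central laboratory".
- Value per subject: the "highest value during the investigational period will be used".
- Denominator: "The denominator for each criterion will be the number of subjects who have at least one value during the investigational period". No laboratory is named.

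The same section adds a plot of peak AST or ALT against peak bilirubin for mirabegron subjects, with the Hy's Law area marked. It gives no separate source rule for the plot.

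Local laboratory data are expected elsewhere in the plan:

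- SAP 6.5.2.1: "In this study laboratory data may come from a central laboratory or a local laboratory, see Table 12 of the protocol". Local values are rescaled by the ratio of the two upper limits and then used for reporting. For normal-range status, "The results from the local laboratory will be used to determine whether a result is outside the normal range".
- SAP 5.4.3: "All clinical laboratory assessments will be performed at a central laboratory or at a local laboratory if results can be made available" to the site.
- Protocol 12.13, Table 12, for hematology and biochemistry: "Visit collection of samples at local facility acceptable if results can be made available to investigative site". These alternate measures "are only permissible in the event of a crisis", after discussion with the medical monitor.
- Protocol 9.5.2: locally obtained values are to be adjusted to the central laboratory, with details left to the SAP.

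**The concern.** The protocol admits local results by adjusting them, and SAP 6.5.2.1 supplies the adjustment. The next SAP section then leaves them out of the liver tables without giving a reason, and nothing later in the SAP brings them back.

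The source rule also sits badly with the peak-value rule. The two can be reconciled only by reading the peak as the highest central value. When the true peak was local, that is not the subject's highest value.

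Three kinds of finding could be missed: a first elevation seen only locally, a local value in a higher category than any central one, and a local bilirubin that would complete a combined criterion. The last includes a bilirubin paired with a central ALT or AST within the 24-hour limit.

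This matters more because the section is the SAP's only dedicated liver summary. Protocol 7.3.6 lists hepatotoxicity as an adverse event of special interest, but SAP 5.4.1 and Appendix 9.2 contain no liver term. With few cases expected, one omission can turn a 1 into a 0.

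**Working it through.** SAP 6.5.2.2 states no event count or precision figure, so there is nothing of the plan's own to reproduce. Three checks apply.

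**1. Does the ULN scaling give a reason to exclude local values?** SAP 6.5.2.1 sets t = x × ULNC / ULNL, where x is the local value and ULNL and ULNC are the local and central upper limits. Dividing by ULNC gives t / ULNC = x / ULNL, so the multiple of the ULN is unchanged. Illustrative values (not from the documents):

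| x | ULNL | ULNC | t | x / ULNL | t / ULNC |
|---|---|---|---|---|---|
| 130 | 40 | 33 | 107.25 | 3.25 | 3.25 |
| 210 | 55 | 40 | 152.73 | 3.82 | 3.82 |
| 100 | 35 | 45 | 128.57 | 2.86 | 2.86 |

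A local value can therefore be placed in every liver category directly as x / ULNL. This shows that the rescaling is neutral. It does not show that local upper limits are as age-specific as the central ones.

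**2. How many subjects could be touched?** Inputs:

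- Two scheduled post-baseline blood draws, at weeks 4 and 12 (protocol 7.2.2).
- At least 92 + 16 = 108 subjects randomized to mirabegron (protocol 9.1).
- Share f of post-baseline draws done locally: not in the documents; assumed 2% to 25%, with draws independent.

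The chance that at least one of two draws is local is 1 − (1 − f)²; that both are local, f². The chance that at least one of three true elevations, each visible at one visit only, is lost is 1 − (1 − f)³.

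| f | At least one draw local | Of 108 | Both local | Of 108 | At least one of 3 cases lost |
|---|---|---|---|---|---|
| 2% | 4.0% | 4.3 | 0.04% | 0.0 | 5.9% |
| 5% | 9.8% | 10.5 | 0.25% | 0.3 | 14.3% |
| 10% | 19.0% | 20.5 | 1.0% | 1.1 | 27.1% |
| 25% | 43.8% | 47.2 | 6.25% | 6.8 | 57.8% |

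For a single such case, the chance of loss is f itself. These figures follow entirely from the assumed f; they show scale and are not an estimate for this trial.

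**3. What happens to the percentage?** Suppose all 108 have a value and the only >3×ULN case has local post-baseline values only. With local values included, the row reads 1/108 = 0.9%. Under central-only it reads 0/107 if that child leaves the denominator, or 0/108 if the child counts as a non-case. The text does not say which. Dropping local values can lower or leave unchanged a count of elevations; it cannot raise it.

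**The case against.** Several points stand in the plan's favour.

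- **Local results are not lost to the report.** A reader might infer that they are. All laboratory data are listed; transformed local values enter the general summaries; and local results decide normal-range status (SAP 6.5.2, 6.5.2.1). Potential Hy's Law cases are reported under the SAE procedures with no condition on laboratory (protocol 12.4.1.2), and confirmed moderate or severe abnormalities require a liver abnormality form (protocol 12.5).
- **A local repeat does not undo a central elevation.** A reader might infer that a child whose repeat was local cannot be counted as >3×ULN. If the first value was central and above the threshold, the child is already counted. The local repeat matters only for a higher category or a bilirubin combination.
- **One local draw does not remove a child from the table.** A child with another central draw in the period stays in. A case is lost only if the finding appears solely in the local sample.
- **Use is exceptional.** Blood tests are central by default, and Table 12 is reserved for a crisis.
- **Central-only can be defended.** It gives one set of reference limits. Protocol 7.2.2 requires age-appropriate norms, and the documents do not show that every local laboratory would supply them. Protocol 12.5 leaves the end-of-study liver analysis to the SAP.

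These points limit the reach of the concern. They do not repair the table, because a listing or an SAE report does not correct a count. Comparability of limits is a reason to flag local values and show a central-only version alongside; it is a weak reason to omit them from the main display.

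**Conclusion.** The point holds as a gap in one set of displays. As written, SAP 6.5.2.2 leaves local values out of the liver categories, the combined criteria and, by implication, the plot, while local biochemistry is permitted and the protocol calls for its adjustment. It also leaves the denominator open for a child with only local post-baseline values.

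The documents do not support saying that the tables will understate liver findings. They could, if an elevation occurs only in a local sample. How often Table 12 would be used is not stated, so the number affected is unknown and may be small. The range of about 4 to 47 of 108 mirabegron subjects with at least one scheduled panel outside the table rests on the assumed 2% to 25% share. Nor do the documents support saying that such a child necessarily drops out of the denominator, since that text names no laboratory. The primary efficacy conclusion is untouched. The change is worth making because the loss can run in only one direction and the remedy is cheap.

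**What to change.** Amend SAP 6.5.2.2 before database hard lock:

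- Classify every result, central or local, as a multiple of the reporting laboratory's own ULN, which equals t / ULNC under 6.5.2.1.
- Include local results in all liver categories, the combined criteria and the plot, flagged by source.
- Define the denominator on the same basis: subjects with any central or local value in the investigational period.
- Keep a central-only table as a sensitivity display.

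The cost is a sentence or two of SAP text and minor programming. No new data item is needed, because the transformation in 6.5.2.1 already requires the local upper limit. The small downside is that local limits may be less comparable or less age-specific; the source flag and the central-only table let a reader see whether that matters.
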